## Criteria for Early Discontinuation

Criteria for Early Discontinuation

### Study Discontinuation

Drop out criteria during the screening and study period include:

- 1) Development of serious psychiatric symptoms as indicated by the Clinical Global Impression (CGI) improvement score of 6 (much worse than baseline) or greater for 2 consecutive weeks.
- 2) If the participant's continued opioid use places him/her at risk for self-destructive behavior or other harm as indicated by a CGI improvement score of 6 or more (much worse than baseline) for 2 consecutive weeks.
- 3) Development of serious medical condition(s) that may or may not be related to study participation (e.g., significant weight loss, serotonin syndrome) as assessed by weekly visits with the psychiatrist, vital sign measurements, weekly weight-ins, and monthly serum and urine laboratory studies
- 4) If the participant becomes pregnant as assessed by monthly urine pregnancy testing

- 5) Weight loss resulting in the participant becoming underweight (BMI<18.5). BMI will be calculated weekly.

Participants may be removed from the trial if they repeatedly miss scheduled appointments or clinical worsening necessitates more intensive treatment (drop out criteria are defined above). Subjects who develop serious psychiatric symptomatology (e.g., psychosis, suicidal ideation, severe depressive symptoms) during the study period will be dropped from the study and appropriate clinical referrals will be made. A patient who's continued opioid use, places them at risk for self-destructive behavior or otherwise places them at significant risk will be discontinued from the study. This would include, but not be limited to, patients who become unconscious after using, engage in destructive or violent behavior while intoxicated, report driving while intoxicated, or develop medical complications from their opioid use. In all cases where subjects are discontinued from the study, the clinical research staff will assume clinical responsibility for the subjects until clinical referrals are operational.

In case that the patient is removed from the research trial for medical reasons, or is requesting withdrawal from the study, he/she will be retained in open treatment for the remaining study period. Upon removal of a patient from the trial due to clinical deterioration, the patient will be referred for appropriate follow-up treatment, in most instances either intensive outpatient or residential treatment. The PI or a study psychiatrist is available 24 hours/day by phone and/or beeper in case of emergency.

## Blood and other Biological Samples

Please create or insert a table describing the proposed collection of blood or other biological specimens

Approximately 10 cc of blood is drawn at screening and at Week 7 (End of Study) for blood chemistries and CBC. A blood serum pregnancy test will be obtained for all female participants during screening. **A urine sample will be collected for a urinalysis at screening. At each study visit a urine sample will be collected for urine toxicology.**

## Assessment Instruments

Create a table or give a brief description of the instruments that will be used for assessment

MINI- International Neuropsychiatric Interview (MINI) (30 minutes; screening)

Risk Assessment Battery (5 min; screening)

Clinical Global Impression Scale- Observer (CGI-O modified from Guy 1976) (5 min; 1x week)

Urine sample for toxicology (5 min; daily)

Hamilton Depression Scale (HAM-D) (5 min; 1x week)

Clinical Opiate Withdrawal Scale (COWS) (2 minutes; 3x/daily during detox, 1x week)

Systematic Assessment for Treatment Emergent Effects (SAFTEE) (3 min; 1x week)

Concomitant Medications Form (3 min; 1x week)

Locator Form (5 minutes; baseline)

The Subjective Opiate Withdrawal Scale (SOWS) (5 min; 1x week )

The State-Trait Anxiety Inventory (STAI) (5 min; 1x week)  
Craving Scale (3 min; daily)  
Vital Signs Nursing Form (3 min; daily)  
Please attach copies, unless standard instruments are used

### Off label and investigational use of drugs/devices

Choose from the following that will be applicable to your study

Drug

Select the number of drugs used in this study

1

#### Drug #1

Name of the drug

Lorcaserin (Belviq)

Manufacturer and other information

Lorcaserin (Belviq) is a weight-loss drug developed by Arena Pharmaceuticals. It has serotonergic properties and acts as an anorexiant.

Approval Status

IND is approved

IND#

134870

Who holds the IND/IND sponsor?

IND is held by PI/CU Investigator

[name], MD

### Research Related Delay to Treatment

Will research procedures result in a delay to treatment?

Yes

Maximum duration of delay to any treatment

Active treatment of known efficacy (detoxification) begins when patients have signed study consent and are randomized to begin outpatient detoxification at STARS. A delay of up to 2 weeks is possible prior to enrollment.

Maximum duration of delay to standard care or treatment of known efficacy

Up to two weeks.

Treatment to be provided at the end of the study

#### Study Discharge/Aftercare Plan:

Discharge and aftercare planning and implementation will be incorporated into the study. A Discharge Plan will be completed by a clinician and approved by a study physician prior to the End of Study visit. After the End of Study, participants will continue in a follow-up phase with once weekly clinic visits with their therapist for up to one month in order to facilitate transition and permit overlap with another treatment

program for aftercare. Discussion of treatment recommendations as well as risks and benefits of accepting and refusing referrals will take place and will be documented.

## Clinical Treatment Alternatives

### Clinical treatment alternatives

The major alternatives for long-term treatment of opiate dependence are "drug-free" treatment on either an outpatient or residential basis, or agonist maintenance with methadone or buprenorphine, all available by referral.

Other options available in the community include either hospital-based detoxification (often agonist-assisted) to a "drug-free" state, which is available to the patients by referral, or outpatient methadone detoxification, which is available at some methadone clinics. Regardless of treatment, the risk of relapse to illicit opiate use is very high once the detoxification is completed without medication-based relapse prevention treatment. XR-naltrexone is FDA-approved for relapse prevention treatment of opiate dependence.

During the initial informed consent process, patients will be informed about alternative treatments and their availability, and that they are free to choose among the options, at baseline or at any time during the study.

## Risks/Discomforts/Inconveniences

Risks that could be encountered during the study period

### Potential Risks

**Study Medication Risks:** One of the main risks associated with participation is drug administration. Lorcaserin (or Belviq©) was approved by the FDA for treating obesity, is generally well tolerated, and has low abuse potential, though it is a schedule IV substance. The target daily dose of lorcaserin in the proposed study (20 mg) is the current FDA approved dose for the treatment of weight management. In clinical trials, headache was the only reported side effect to occur at a frequency much greater than placebo. Other possible side effects of lorcaserin include: constipation, dry mouth, headache, nausea, and dizziness. Some rare but serious side effects include hypoglycemia in patients with Type 2 diabetes, serotonin syndrome, agitation, confusion, hallucinations, arrhythmias, cardiac valve disease, depression, thoughts of suicide, and an erection lasting longer than 4 hours.

The combination of lorcaserin with other serotonergic medications (e.g., 5HT3 antagonist antiemetics, bupropion, triptans, SSRIs, SNRIs, TCAs, St. John's Wart, tryptophan), medications that impair the metabolism of serotonin (e.g., MAO inhibitors, dextromethorphan, tramadol, lithium), or antidopaminergic medications (e.g., antipsychotics) may enhance serotonergic effects, and this could result in rare but serious serotonin syndrome reaction. Signs of serotonin syndrome include: mental

status changes (e.g., anxiety, agitated delirium, restlessness, and disorientation); easy startle, autonomic manifestations (e.g., diaphoresis, tachycardia, hyperthermia, hypertension, vomiting, and diarrhea); and neuromuscular hyperactivity (e.g., tremor, muscle rigidity, myoclonus, hyperreflexia, and bilateral Babinski sign).

The combination of lorcaserin with ergot derivatives is contraindicated. The use of these drugs together may increase the risk of developing valvular heart disease in addition to enhancing serotonergic effects that may result in serotonin syndrome. The combination of lorcaserin with 5HT2B-R agonists (e.g., cabergoline) is contraindicated due to the increased risk of cardiac valvulopathy. Lorcaserin is a moderate CYP2D6 inhibitor and may decrease the clearance of drugs metabolized by CYP2D6, and thus raise these other drug levels increasing the risk of toxicity. Lorcaserin is contraindicated in pregnancy due to the fact that weight loss offers no clinical benefit in pregnancy and is advised against.

**Risks of the Buprenorphine-Clonidine-Naltrexone Procedure:** In this procedure, opiate-dependent patients are stabilized briefly on the partial opiate agonist buprenorphine. During subsequent administration of naltrexone and throughout the detoxification, withdrawal symptoms are treated with clonidine, an alpha-2-adrenergic receptor agonist which reduces sympathetic nervous system output produced by opiate withdrawal, clonazepam, a benzodiazepine which reduces the anxiety and dysphoria and permits sleep, and other prn medications such as zolpidem for insomnia. Opiate withdrawal causes agitation, elevated pulse and blood pressure and other signs of sympathetic arousal, and sometimes confusion. Clonidine may produce somnolence or hypotension. Clonazepam commonly may produce somnolence. The procedure is conducted in a setting equivalent to a day hospital, with a STARS study physician present at all times, to permit close monitoring of vital signs and mental status. Naltrexone does not provide a blockade for other substances of abuse, such as cocaine, benzodiazepines, or alcohol. Thus, patients remain at risk of experiencing intoxicating effects and/or overdose with these drugs. This risk is highlighted in the consent form. Rare cases of allergic pneumonia following depot administration have been reported. Patients are advised of this in the consent form and are urged to contact STARS staff immediately if they develop any trouble breathing. We have observed two cases of allergic hives in patients treated with naltrexone. This risk is highlighted in the study consent form.

**Side Effects of Naltrexone:** Naltrexone has been associated with reversible hepatocellular injury indicated by elevated liver enzymes when administered at doses substantially greater than the 50mg per day dose recommended for maintenance treatment of opiate dependence and proposed for the present studies. When used in the recommended dose range in opiate-dependent patients, this risk is remote (Brahen et al., 1988). Naltrexone is therefore contraindicated in patients with acute hepatitis or liver failure, and such patients are excluded from the study. Patients with hepatic enzyme levels greater than 3 times the upper limit of normal are therefore excluded. XR-naltrexone achieves higher blood levels than oral naltrexone initially, but these should remain lower than levels associated with hepatitis. If naltrexone-induced hepatitis were to occur during treatment with naltrexone injections, where the naltrexone would be only very slowly eliminated, this would prolong exposure to the offending agent. However, the experience with long-acting injectable naltrexone also suggests it is safe. In our studies with long-acting naltrexone several patients experienced elevation in liver enzymes, which were determined to be related to hepatitis C. One patient in the XR-naltrexone trial developed diabetes mellitus, which was deemed unlikely to be study related.

During the outpatient detoxification phase of the study, patients will have daily doses of oral naltrexone supervised at STARS. If a patient misses one or more oral naltrexone doses and resumes regular opiate use, then taking a dose of naltrexone will precipitate opiate withdrawal, which may be quite severe. Patients will be warned not to take the naltrexone if they have missed their dose for more than three days in a row and resumed opiate use for more than one day. Patients will be advised to report to STARS for clinical assessment by a study physician. If history and urine toxicology findings suggest a lapse or possible relapse, a naloxone challenge may be necessary. If the naloxone challenge is positive (withdrawal is precipitated), then the patient will be managed according to guidelines described above (see section entitled Handling of Lapses and Relapses). Relapsed patients who cannot resume naltrexone are referred for inpatient detoxification or outpatient buprenorphine or methadone maintenance.

Self-administration of large doses of opiates may override the blockade produced by naltrexone, resulting in opiate overdose with its attendant risks including respiratory depression and death. Patients will be warned of the severe danger of trying to override the blockade. Also patients who have stopped naltrexone for several days and resume opiates will not be tolerant initially, so that the quantities of opiates self administered prior to treatment, when they were tolerant, may be quite dangerous in the non-tolerant state. Patients will be warned of this. Patients with a history of drug overdose in the past 3 years or an overdose after detoxification within 10 years will be excluded. Patients who self-administer opiates to the point of somnolence or stupor will be removed from the trial and referred to inpatient detoxification or to methadone maintenance treatment. It is notable that XR-naltrexone in theory might protect against this risk, since naltrexone blood levels decline gradually over a period of weeks rather than the abrupt decline which occurs when oral naltrexone is discontinued. In the event of a medical emergency requiring opiate analgesia, a patient on naltrexone will require higher doses of opiates than normally administered. Patients will be informed of this and will be given a naltrexone medication card to carry in their wallet.

**Pregnancy:** Both the buprenorphine-clonidine-naltrexone procedure and naltrexone maintenance are considered contraindicated in pregnancy. Several small case series (Hulse et al., 2001; 2004) are reassuring in suggesting favorable pregnancy outcomes in women detoxified and maintained on naltrexone while pregnant. However, standard practice suggests methadone or buprenorphine maintenance is the treatment of choice for opioid dependent pregnant women, and we do not consider the small size of these case series sufficient to amend that recommendation. Absence of pregnancy will be confirmed at baseline and monthly during the study with urinary HCG. For women, regular use of an adequate contraception method (diaphragm with spermicide, condom with spermicide, birth control pills) is required for inclusion in the study.

**Other Risks:** Blood draws may cause slight discomfort at the site of needle entry, can result in infection at the site if hygienic/sterile techniques aren't used, or can result in a small bruise.

Participants will receive cash compensation and incentives during the study that could pose a risk of providing more available funds to purchase illicit opioids.

The structured interviews, rating scales, and questionnaires should add no physical risk. The major disadvantage is the time required to complete them and that some of the questions might be embarrassing to participants. Our past experience with these measures indicates that they are acceptable to participants.

However, some people have found them uncomfortable and/or tiring because the interviews/assessments are long and of a personal nature.

Describe procedures for minimizing risks

### **1) Screening Procedures**

In order to minimize the risk associated with the study, subjects undergo a comprehensive medical and psychiatric evaluation during the screening procedure. The baseline medical evaluation consists of a physical examination, blood chemistry profile (including liver function tests), complete blood count, urinalysis, serum pregnancy test, urine toxicology and is designed, along with the clinical history, to detect chronic and/or unstable medical illnesses. A comprehensive psychiatric assessment is performed during the screening process, and is intended to detect and assess all past and current psychiatric disorders. The eligibility criteria (see above) are designed to minimize the medical and psychiatric risks to participants by excluding those for whom participation would place them at an increased risk. Special attention will be given to patient's concurrent use of medications. Participants on medications that meet exclusion criteria will not be included in the study. If participants have recently completed another study at STARS, we will ensure, as with other medications, that there are no drug-drug interactions with the possible recent exposure to other study medications or will ensure proper time for wash-out between studies.

### **2) Study Procedures**

Participants will be informed about the possible side effects and risks (listed above) of taking lorcaserin both alone and in combination with other medications through extensive discussions with staff psychiatrist during the consent process. Participants will be told to contact the clinic if they experience any adverse effects and given the number for the 24-hr physician on-call. All participants, both those not taking and taking concurrent medications, will be monitored closely throughout the study for possible signs and symptoms of serotonin syndrome and weight loss. Participants' mental status and physical health are monitored weekly during the study period by a psychiatrist. Vital signs will be obtained at each study visit. Weight will be assessed weekly to monitor for possible excessive weight loss and used to calculate BMI. At clinic visits, a physician will assess participants for signs and symptoms of adverse effects of lorcaserin, noting which if any symptoms are present, the severity of the symptoms, make adjustments to study medication dose, discontinue study medication, or withdraw the participant from the study if needed.

Female participants who are engaging in sexual activity with men must use adequate methods of contraception which will be discussed repeatedly during the screening process. Serum pregnancy tests will be conducted during screening and urine pregnancy tests will be performed monthly during the study. If a female participant does become pregnant or wishes to become pregnant, study medication will be immediately discontinued, she will be withdrawn from the study, and offered continuing nonpharmacological treatment (psychotherapy).

### **3) Procedures to Minimize Other Risks:**

With regards to the risks of blood draws, only staff trained in phlebotomy will draw blood from participants to minimize risks of infection. Participants will be warned of the possible associated discomfort and slight bruising following blood draws. They can decline blood draws at any time.

We aim to reduce the risk of using cash reimbursements and incentives to buy drugs by keeping reimbursements at a low monetary value. The monetary incentives for completion of study related activities are felt to be modest, appropriate, and limited. This payment schedule has been used successfully in treatment studies in our clinic and others with no observed effect of increased drug use.

With regards to risks associated with interviews, rating scales, and questionnaires, patients are informed that they may refuse to answer any questions and may ask to stop at anytime. If participants become upset during the interviews/assessments, assistance will be made available to them.

## Methods to Protect Confidentiality

Describe methods to protect confidentiality

In the course of treatment, patients may divulge information which is sensitive and may have adverse social consequences if released. This would include information released to insurance companies, family members, or made public in any way. Patient records are kept in locked files and released only with the patient's consent. Contact with family members or significant others is made only with the patient's express consent. All mainframe computer and microcomputer data is stored without names or other uncoded identification. Patients will be identified only through a numerical code in both the mainframe and microcomputer databases, while a paper code list will be kept under lock and key by the PI and the Research Assistant. A Federal Certificate of Confidentiality will be obtained.

*Will the study be conducted under a certificate of confidentiality?*

Yes, we will apply for the Certificate of Confidentiality

## Direct Benefits to Subjects

Direct Benefits to Subjects

Participants will receive up to 12 weeks of free treatment. A complete physical and psychiatric evaluation will be performed free of charge.

## Compensation and/or Reimbursement

Will compensation or reimbursement for expenses be offered to subjects?

Yes

Please describe and indicate total amount and schedule of payment(s).

Include justification for compensation amounts and indicate if there are bonus payments.

During the study, participants will be given **\$20 for each study visit**. Additionally participants will receive \$10 for returning study medication bottles (5 weeks of study medication) . Participants could earn as much as \$410 total over the course of the study.

## Uploads

Upload the entire grant application(s)

Upload copy(ies) of unbolded Consent Form(s)

Lorca +nr-ntx cf\_5.5.17 unbolded.pdf

Upload copy(ies) of bolded Consent Form(s)

Lorca +nr-ntx cf\_5.5.17 bolded.pdf

Upload evidence of FDA IND approval(s)

IND to IRB.pdf

Upload copy(ies) of the HIPAA form

LOCRA + XRNTX HIPPA.pdf

Upload any additional documents that may be related to this study

ind decision worksheet\_vivitrol.pdf

Lorcaserin in Combination with XR COVER SHEEt\_4.24.17\_UNBOLDED.pdf

Lorcaserin in Combination with XR COVER SHEEt\_4.24.17\_BOLDED.pdf

## Data analysis

All participants were randomized 2:1 lorcaserin to placebo and stratified by severity of use (Low:  $\leq 200$  mg or  $\leq 5$  bags vs. High:  $> 200$  mg or  $> 5$  bags). The randomization scheme was skewed toward the experimental group in order to maximize the amount and precision of information on the feasibility of lorcaserin treatment. All participants were block randomized with randomly selected blocks of size three, six, and nine. The randomization sequence was designed by an independent statistician and utilized by the research pharmacist. Participants and all other study staff were blind to treatment assignment.

The primary outcome is successful induction onto XR-NTX. Secondary outcomes are: (a) severity of acute withdrawal during detoxification and induction prior to the first injection, and (b) and receiving the second injection of XR-NTX.

The outcomes of successful induction onto XR-NTX and receiving 2nd injection will be analyzed in SAS® using logistic regression with predictors: treatment (lorcaserin vs. placebo), age, baseline severity of use (high vs. low), and opioid type. A 4-level categorical predictor will be created to represent opioid type (heroin vs. opioid pills) and whether subjects were fentanyl positive at baseline. The categories are: (1) fentanyl-positive heroin, (2) fentanyl-negative heroin, (3) fentanyl-unknown heroin, and (4) fentanyl-negative opioid pills (reference group).

Withdrawal during the induction period, as measured by COWS and SOWS, will be analyzed using longitudinal mixed effect models with a random intercept for participant and an autoregressive correlation structure (AR1) to account for the within subject correlation. Predictors included: treatment, time, and time-by-treatment two-way interaction, adjusted by the baseline withdrawal score, age, baseline severity of use, and opioid type.

Retention to study week 8 and time to drop out will be compared using Kaplan-Meier curves and Cox proportional hazard models.

All analyses described in the preceding sections will be conducted on the intent-to-treat sample of all randomized participants with 2-tailed tests and a significance level of 5%.

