## Lay Summary of Proposed Research

Lay Summary of Proposed Research

We propose to recruit patients with **Opioid Use Disorder (OUD)** seeking treatment into our program of outpatient detoxification and naltrexone induction followed by a relapse-prevention treatment with **Extended release-naltrexone (XR-NTX)**. Eligible participants will be randomly assigned to adjunctive treatment with lorcaserin (N = 40), or placebo (N = 20) with weekly therapy. Lorcaserin **or placebo** 10 mg bid will be started on Day 1 of the study to address acute withdrawal, then maintained over the next 5 weeks, and stopped after the second XR-naltrexone is administered. Patients will be seen twice weekly for monitoring and offered two injections of naltrexone; at the end of oral naltrexone induction (end of week 1) and four weeks later (week 5). The primary outcome measure will be the proportion of patients successfully retained to receive the second naltrexone injection. Patients retained to this point tend to stay on treatment and do well long term, hence this is the most clinically relevant outcome to evaluate treatment initiation.

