## Background, Significance and Rationale

Background, Significance and Rationale

Opioid Use Disorder (OUD) has reached epidemic proportions in the US with more than 2.5 million individuals affected, and substantial morbidity, including fatal overdose, now a leading cause of accidental death. Ironically, while opioid dependence is among the most severe addictions, it also has the most effective medication treatments. Yet, most patients with OUD are not engaged in any form of treatment and those in treatment do not continue with the medication for a sufficient period of time to assure sustained abstinence. The immediate goal of this proposal is to help improve the acceptability and effectiveness of the new treatment strategy, opioid withdrawal followed by a relapse prevention using extended-release injectable formulation of naltrexone (XR-naltrexone), in order to ultimately expand the availability of effective treatment options for opioid dependence.

The recent advent of XR-naltrexone has improved adherence to naltrexone and approximately 50% of patients started on injectable naltrexone are successful in treatment at 6 months, comparable with outcome of buprenorphine-assisted treatment but with lower rates of continuing opioid use. However, in order to safely initiate treatment with XR-naltrexone, an opioid dependent patient needs to undergo opioid withdrawal (detoxification) and be rapidly inducted onto the medication, which involves additional withdrawal discomfort. We developed an outpatient detoxification and naltrexone induction procedure, which has high patient acceptability and success rates, but the problems of withdrawal discomfort, persistent craving, and resulting dropout before the first XR-naltrexone dose persist. We have also shown that in addition to acute opioid withdrawal during the induction, subacute withdrawal symptoms, craving, and insomnia persist during the first several weeks after the first XR-naltrexone dose and may contribute to early dropout (after 1-2 injections). Thus, withdrawal discomfort and persistent craving is a likely common element underlying both failure of induction and early attrition from naltrexone treatment.

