## Specific Aims and Hypotheses

## Specific Aims and Hypotheses

Specific Aim #1: To determine whether lorcaserin, compared to placebo, increases the proportion of patients successfully inducted onto injectable naltrexone and retained to receive the second monthly injection.

Specific Aim #2: To determine whether lorcaserin, compared to placebo, reduces severity of acute withdrawal and craving during detoxification and induction prior to the first injection and protracted withdrawal after the first injection.

This will be the first clinical trial of lorcaserin for treatment of opioid withdrawal and the facilitation of naltrexone induction. If found effective, adjunctive lorcaserin would be a significant advance in the initiation of treatment with XR-naltrexone. As such, this method would have the potential to expand the population of individuals with OUD for whom naltrexone is a viable treatment option.

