### Study Procedures

Describe the procedures required for this study

Potential subjects will undergo a screening visit which will include a demographics questionnaire, medical history, physical examination, psychiatric evaluation, laboratory testing, and electrocardiogram. The MINI International Neuropsychiatric Interview (MINI) will be conducted to determine current DSM-5 diagnoses. Eligible participants will be offered the opportunity to participate in the research treatment study and informed consent using the IRB-approved consent form will be obtained by the research psychiatrist.

This is a 2-arm, randomized, placebo-controlled trial to obtain initial data regarding **feasibility and tolerability** of lorcaserin for increasing successful initiation onto XR-naltrexone. Sixty volunteers will be offered outpatient detoxification followed by a treatment with XR-naltrexone. Participants will be offered two injections of XR-naltrexone and weekly therapy. We selected adherence with naltrexone injections as the primary outcome because it is the most clinically meaningful outcome of this treatment.

The study will be entirely outpatient. Upon study entry, participants will begin clinic visits at the Substance Treatment and Research Service (STARS) clinic. All participants will visit the clinic twice weekly to

provide urine toxicology, report on adverse events, and complete additional assessments (Table 1), All participants will also receive medical management, a medication adherence focused psychosocial intervention that facilitates compliance with study medication and other study procedures, and promotes abstinence from opioids and other substances.

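### The SAP's primary outcome is induction onto XR-naltrexone; the protocol's is receipt of the second injection, which the SAP ranks as secondary

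*SAP*

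**What the plan says.** **SAP, Data analysis:** "The primary outcome is successful induction onto XR-NTX". Receipt of the second injection is secondary outcome (b). Both are analysed by logistic regression on treatment, age, baseline severity and opioid type, in all randomised participants, two-tailed at 5%. Retention to week 8 and time to drop-out are also analysed.

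**Protocol, Lay Summary:** "The primary outcome measure will be the proportion of patients successfully retained to receive the second naltrexone injection". The reason given is that patients who reach this point tend to stay in treatment and do well: "hence this is the most clinically relevant outcome to evaluate treatment initiation". The first injection is placed at the end of week 1 and the second four weeks later.

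**Protocol, Specific Aims:** Aim 1 asks whether lorcaserin "increases the proportion of patients successfully inducted onto injectable naltrexone and retained to receive the second monthly injection".

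**Protocol, Study Procedures:** the wording is looser. "We selected adherence with naltrexone injections as the primary outcome because it is the most clinically meaningful outcome of this treatment". The same section describes the trial's purpose in terms of successful initiation onto XR-naltrexone, which is the protocol wording closest to the SAP.

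**The concern.** The primary outcome decides which test carries the trial's main claim. Here each document names a different one, and the SAP ranks the protocol's primary as secondary. The two outcomes are nested: a second injection presupposes a first. They differ for everyone who is inducted and then lost before week 5.

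The protocol's rationale covers both stages. Its Background says: "Thus, withdrawal discomfort and persistent craving is a likely common element underlying both failure of induction and early attrition from naltrexone treatment". An outcome settled at about the end of week 1 cannot register an effect on the later attrition. The SAP's Data analysis section has no multiplicity rule, so a reader cannot tell which of the two 5% tests is the confirmatory one.

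Two definitions are also missing from that section. It does not say explicitly what counts as successful induction. Nor does it say by when a second injection must be given to count, although the protocol's Study Procedures allow a missed injection to be rescheduled.

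**Working it through.** **1. Can the texts be read as agreeing?**

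| Place | Primary outcome or aim |
|---|---|
| Protocol, Lay Summary | Receipt of second injection |
| Protocol, Specific Aim 1 | Inducted and retained to second injection |
| Protocol, Study Procedures | Adherence with injections (two are offered) |
| SAP, Data analysis | Successful induction; second injection is secondary (b) |

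The SAP lists and models the second injection separately, so its induction outcome cannot include it. No protocol section makes induction alone the primary outcome. Neither text is an amendment log.

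The documents state no power or assumed response rate for either outcome, so there is no sample-size figure to reproduce and none that shows which outcome was intended. The figures below are illustrations on assumed rates.

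**2. Participants whose status changes.** Let p be the proportion inducted and q the proportion of those who receive the second injection. The number who are a success under the SAP and a failure under the protocol is 60 × p × (1 − q), with 60 = 40 + 20 from the Lay Summary. Assume p = 0.50–0.75 and q = 0.60–0.80.

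- Minimum: 60 × 0.50 × 0.20 = 6.
- Maximum: 60 × 0.75 × 0.40 = 18.

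**3. How often the two tests disagree.** 20,000 simulated trials per scenario, 40 versus 20, nested binary outcomes, the SAP's logistic predictors, two-sided Wald test at 5%. Assumed: severity split 50:50, four equal opioid types, no covariate effects. Rates are lorcaserin/placebo in %. These scenarios extend beyond the range used in step 2.

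| Induction | Second, given induction | Power, induction | Power, second injection | Trials disagreeing |
|---|---|---|---|---|
| 80/50 | 85/65 | 0.642 | 0.732 | 0.230 |
| 70/50 | 80/65 | 0.326 | 0.400 | 0.244 |
| 75/55 | 80/65 | 0.346 | 0.423 | 0.249 |
| 80/60 | 80/60 | 0.371 | 0.523 | 0.297 |
| 85/65 | 85/65 | 0.406 | 0.605 | 0.315 |
| 75/60 | 80/70 | 0.225 | 0.260 | 0.198 |
| 90/70 | 85/65 | 0.436 | 0.643 | 0.337 |

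Across these rows, 12–27% of trials are significant on the second injection only and 6–9% on induction only. With no effect at either step (induction/second given induction of 50/60, 60/60 and 75/80, the same in both arms), the tests disagree in 0.077, 0.079 and 0.067 of trials. No simulated trial had both outcomes significant in opposite directions.

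A second run of 4,000 trials per scenario gave 0.226 (80/50; 85/65), 0.314 (80/60; 80/60), 0.188 (75/60; 80/70), 0.350 (90/70; 85/65) and 0.084 (no effect, 60/60), all close to the values above.

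**4. Error rate if either result could be claimed as primary.** If the tests were independent: 1 − 0.95² = 0.0975. The upper bound is 0.05 + 0.05 = 0.10. The outcomes are positively related, so the true figure should be below 0.0975.

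**The case against.** The strongest reply is that little turns on the label. The protocol calls this a pilot, proof-of-concept trial gathering initial data on feasibility and tolerability. Both outcomes are specified with the same model, population and significance level, and a reader given both results is misled about neither. That is correct and limits the harm: no information is lost. It does not say which result is primary, and the SAP does apply 5% tests.

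Four narrower points have force.

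- **Direction.** The excess of trials significant only on the second injection depends on assuming benefit at both steps. If lorcaserin helps induction only (80/50, then 70/70), about 37% of trials disagree: about 33% are significant on induction only and 3% on the second injection only. The direction is an assumption; the disagreement remains, and is larger.
- **Top of the range.** In the 90/70 scenario, about 30% of re-run trials had a very large coefficient, a sign of separation, where Wald tests are unreliable. The 34% figure is therefore soft.
- **Definition of induction.** The SAP's reference to induction before the first injection points to receipt of that injection as the intended meaning. The gap is a clarification rather than a fault that affects the result.
- **Sequence.** Part of the SAP was not in the text supplied for review and could hold a date or a reason. Nothing can be concluded about when or why the difference arose. Even a stated reason would leave the current protocol and SAP in conflict.

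**Conclusion.** The contradiction stands on the text alone and must be fixed; confidence is high. The two primary outcomes are settled about four weeks apart and classify differently every participant who is inducted but does not receive a second injection. Whether the trial meets its primary outcome can therefore depend on which document is followed.

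The figures of 6–18 participants and 20–34% of trials rest entirely on assumed rates and serve only to show that the difference is not negligible at this sample size. They do not show which outcome would favour lorcaserin.

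**What to change.** Name one primary outcome in both documents.

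- **Default:** use the protocol's outcome in the SAP, that is, receipt of the second injection among all randomised participants, with no second injection counted as failure. State an analysis window for when it counts. This is a counting rule only and changes nothing about when injections are given. Define successful induction as receipt of the first injection and make it the first secondary outcome, with the same regression. Align the looser wording in the protocol's Study Procedures.
- **If induction is meant to be primary:** amend the protocol's Lay Summary, Specific Aims and Study Procedures to match, and report the second-injection result with equal prominence, identified as the primary outcome stated in the protocol reviewed here.

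In either case, record when and why the two documents came to differ and whether treatment assignments had been unblinded by then. If they have been, state that in the report, because any choice made now would be made with results available.

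The cost is a SAP revision or a protocol amendment with a dated rationale. No new data or participants are needed.
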